## Research Protocol: Healthy Lifestyle Prenatal Care Study

### Aims:

**Specific Aim 1.** Use a RCT to evaluate the short- and more long-term efficacy of the COPE-P program to improve healthy lifestyle behaviors (nutrition and exercise), psychosocial health, and birth and post-natal outcomes in pregnant emotionally distressed minority women as compared to an attention control group.

**Hypotheses 1a (primary outcomes).** Immediately after the COPE-P program, at 4-6 weeks postpartum (3 months post intervention), and at 6 months postpartum (8 months post intervention), COPE-P participants will report higher healthy lifestyle behaviors, and less anxiety, stress and depressive symptoms than will the attention control participants.

**Hypothesis 1b (secondary outcomes).** COPE-P participants will demonstrate more appropriate pregnancy weight gain, better birth outcomes (mode of delivery, birth weight, and gestational age), more appropriate postpartum weight loss, and better breastfeeding outcomes than attention control participants.

**Specific Aim 2.** Examine the role of cognitive beliefs and perceived difficulty in leading a healthy lifestyle in mediating the effects of the COPE-P program on healthy lifestyle behaviors and psychological symptoms in minority pregnant women.

**Hypothesis 2 (theory building exploratory).** The effects of the COPE-P program on participants' healthy lifestyle behaviors and levels of anxiety, stress and depressive symptoms will be mediated by beliefs about their ability to make healthy lifestyles choices and their perceived difficulty in leading a healthy lifestyle.

**Exploratory Aim.** Explore characteristics that may moderate healthy lifestyle behaviors, psychosocial health, and birth and post-natal outcomes (e.g., race/ethnicity, income, age, parity, language, level of education, marital status).

**Research Question:** What is the short and long-term effect of the COPE-P program in high-risk pregnant minority women receiving prenatal care on healthy lifestyle behaviors (nutrition and exercise), psychosocial health (healthy lifestyle beliefs, healthy lifestyle behaviors, anxiety, stress and depression), and birth and post-natal outcomes (gestational age at birth, gender, birth weight, birth length, overall health, mode of delivery, breastfeeding (initiation and duration) versus an attention control group (PregnancyPlus group).

**Overview of the design.** The study conducted will be a longitudinal randomized block RCT with repeated measures (beginning with screening prior to 19 weeks, group prenatal care in both groups (COPE-P intervention group and PregnancyPlus attention control group) from  $16 \pm 2$  to  $31 \pm 2$  weeks and ending at 6 months postpartum). We will block on race/ethnicity to ensure equal numbers of Hispanic and Black women in the COPE-P and PregnancyPlus groups. There will be a total of 30 groups over the course of the study. There will be 22 English speaking groups and 8 Spanish-speaking groups. We will consent and screen up to 700 women, knowing that approximately half will screen out. In order to achieve our target of 182 Black or Hispanic women who complete the study, and accounting for a 30% attrition rate, we will enroll up to 236 women who screen in at Jacobi Medical Center. Four groups (of at least six women per group) will run in each 18-week time segment (COPE-P intervention is six sessions each three weeks apart). The PregnancyPlus group also will have six group prenatal care sessions each three weeks apart. Each session is 1 hour and 30 minutes to 1 hour and 45 minutes in length. Each group within the 18-week time segment will be randomly assigned (using a sealed envelope technique) as either a COPE-P or PregnancyPlus group. At Jacobi Medical Center in Bronx, NY, for each 18-week time segment, there will be two control groups and two intervention groups. The intervention and attention control groups programming will be delivered in Group Prenatal Care methodology which begins in the second trimester consisting of at least 6 women per group. Participants (18 – 40 years) will be screened prior to their 19th week of pregnancy and recruited into the study from the antepartum clinic.

If a participant does not screen into the study, she will be thanked for her time and interest and paid \$10.00 for her participation in the screening process.

07/30/2021

If a woman does screen into the study, she will provide further baseline data at this point. In addition to the screening tools, baseline data will include: demographic and personal information, weight from clinic scale, a 24 hour diet recall, the Healthy Lifestyle Beliefs Scale and the Healthy Lifestyle Behaviors Scale. A participant will then be assigned to the next available group based on fetal gestational age (groups having been scheduled and previously randomized as intervention or control as described above). In the event that group prenatal care is not feasible, the group sessions can be conducted as virtual visits (Zoom or Facetime etc.) or content can be provided in a 1:1 patient to provider setting. Participants will then be given an appointment for their first group prenatal care session and a Fitbit Flex 2, instructions on how to immediately begin using the Fitbit (to provide baseline data that will be uploaded at the first group session) and a Fitbit number (for confidentiality) so that they can compare with other pregnant women. All participants will receive \$30.00 for at the baseline visit (**T0**).

All women in this study will receive 6 sessions of group prenatal care beginning at 16 weeks gestation ( $\pm 2$  week) and ending at 31 weeks ( $\pm 2$  week). At 16 weeks gestation, women receive care every three weeks. The timing of our group prenatal care is designed around prenatal testing to decrease participant burden. We will begin at 16 weeks when all women in care have alpha-fetal protein screening drawn. The second session is at  $19 \pm 2$  week, when women are normally receiving an anatomy sonogram. The third session is  $22 \pm 2$  weeks, which is not associated with any specific prenatal care milestones. The fourth session is  $25 \pm 2$  week is associated with third trimester labs and the glucose tolerance test. The fifth session at  $28 \pm 2$  weeks and the sixth session at  $31 \pm 2$  week are not associated with specific prenatal care milestones. Therefore, 3 of the 6 sessions have standard prenatal testing associated with them (encouraging attendance).

**COPE-P intervention group:** The COPE-P intervention group will receive the COPE-P Intervention over the 6 sessions of group prenatal care. Each session lasting for 1 and a half hours.

Session 1 of COPE-P focuses on the thinking, feeling and behaving triangle, and the ABCs (A=Antecedent or Activator event, B=Belief that follows the event, C=Consequence: how you feel and how you behave). The thinking, feeling and behaving triangle and the ABCs are reinforced throughout the program and examples for use are based on peer input.

Session 2 of COPE-P focuses on self-esteem and positive self-talk, including ways to build self-esteem and the group provides examples of how to change unhealthy habits into healthy ones. Signs of poor and healthy self-esteem are discussed. Discussion of healthy eating and active living is integrated throughout Session 2. Nutrition content includes information on reading labels. Skills building activities for Session 2 include changing an unhealthy habit into a positive one.

Session 3 of COPE-P focuses on stress and coping during pregnancy. Physical and emotional responses to stress are discussed along with healthy snacking. Examples of healthy ways to cope with typical stresses are solicited. Signs of depression and anxiety are elicited and the group problem solves positive strategies to deal with depression, anxiety, and stress. This skills building session focuses on recognizing unhealthy ways of coping and examples of how to unhealthy coping into healthy coping strategies.

Session 4 of COPE-P focuses on planning, goal setting and the 4-step problem solving process, including overcoming barriers related to eating. The skills building activity for Session 4 focuses on developing strategies for overcoming barriers and problem solving a current challenge.

Session 5 of COPE-P focuses on dealing with emotions in healthy ways through positive thinking and effective communication. Women practice regulating their emotions along with mental and guided imagery. Positive self-control strategies for emotions and unhealthy eating are explored. The skills building activities in this session focus on practicing mental imagery and monitoring for emotional triggers with a response plan.

07/30/2021

Session 6 of COPE-P focuses on coping with stressful situations commonly encountered during pregnancy while continuing to reinforce the thinking, feeling, and behaving triangle. Influences on healthy eating are explored. In skills building activities, women practice positively dealing with challenging situations

**PregnancyPlus Attention Control Group:** At each group session, the PregnancyPlus attention control group will receive the prenatal care described under standard care performed by certified nurse midwives. Additionally, each week for six weeks, they will discuss a pamphlet designed for patient education by ACOG. These six pamphlets are: 1) Nutrition during pregnancy 2) Exercise during pregnancy 3) Obesity and pregnancy 4) Exercise after pregnancy 5) Breastfeeding your baby 6) Routine Tests during Pregnancy. At each group prenatal care session, routine obstetric assessment (blood pressure, pulse, weight, BMI, urinalysis for glucose and protein, auscultating fetal heart tones, and uterine size assessment) will be performed. Routine discomforts of pregnancy, smoking cessation, and danger signs of pregnancy will be discussed. Women will return to receiving individualized standard prenatal care at the end of the 6 sessions. [name] will conduct the training of the attention control group midwives and [name] will conduct the training of the intervention group midwives. The same protocol for assessing fidelity will be used for COPE-P and PregnancyPlus.

Different care providers will run the COPE-P and PregnancyPlus groups, assuring that there is no carryover effect of the intervention into the control group.

In addition to baseline assessments, at the end of the 18-week timeframe and at their last group prenatal care session, all women will complete the GAD-7, PSS, EPDS, a 24 hour diet recall, the Healthy Lifestyle Behaviors Scale and the Healthy Lifestyle Beliefs Scale. Fitbit data and weight also will be obtained. In the intervention group, participants also will complete the COPE-P evaluation. This data will be **T1**, and will be collected at approximately 31 weeks gestational age. For women who miss this visit, data will be collected at the next scheduled prenatal visit. Participants will be compensated \$30 for their study participation.

Three months after the intervention (approximately 4-6 weeks postpartum - **T2**), all women will be contacted and will once again complete all measures, as well as an infant data form, at the routine postpartum visit. Participants will receive \$40.00 for their participation.

At eight months post intervention (**T3** - six months postpartum at the six-month well baby visit), all women will once again be contacted and complete all measures (including weights taken on available pediatric clinic adult scales –same model as prenatal scales). Participants will receive \$50.00 for their participation. Outcome data from charts will be collected by team members blind to group assignment.

If study visits cannot be conducted face-to-face, data will be collected through telehealth methods such as via phone or video call (Zoom or Facetime etc.).

**Sampling.** Women will be recruited from the antenatal clinic if they are: between 18 and 40 years old, in their first trimester with an uncomplicated singleton pregnancy of less than 19 weeks, and self-identify as either Black or Hispanic and can read and speak English or Spanish. A completed sample size of 182 Black and Hispanic women from JMC in the Bronx and 182 Black and Hispanic women from OSU Total Health and Wellness clinics will be required to meet the determined sample size of 364 total (at 4 data collection points for each, resulting in ~1,450 observations). This will have greater than 80% power to detect small to moderate effects (i.e. 25 or greater) between group differences in healthy lifestyle behaviors, psychosocial health, and outcomes testing at alpha = .05 for all proposed models. The sample of 364 will have > .80 to detect a small to medium mediated effect. The sample of 364 will have > .80 to detect a small to medium mediated effect.

**Setting. Jacobi Medical Center** is part of New York City Health + Hospitals (NYC H + H), the largest municipal hospital system in the United States. New York City Health + Hospitals oversees the public health care system in all the five boroughs that comprise New York City. It provides one-fifth of the total number of discharges and more than one-third of the emergency services and hospital-based clinic visits in all of New York City. Jacobi Medical Center is an academic affiliate of the Albert Einstein College of Medicine. Jacobi Medical Center is located in the Bronx. As one of the largest health care delivery facilities in the Bronx and in New York City, Jacobi Medical Center has developed a world- wide reputation of distinction. It is renowned for its primacy in

07/30/2021

the delivery of emergency and trauma services, has developed an image of excellence as a provider of choice subspecialty care, and is widely recognized for its devotion to the health care needs of the large and diverse community it serves. The Bronx population represents a wide range of racial and ethnic diversity with 43.4% of the population being African-American and 55% of the population being Hispanic, adding up to more than 100% as Hispanics may be of any race and are also included in the applicable race category by the U.S. Census Bureau (2015). Jacobi Medical Center is an urban medical center, which serves a population of 1.3 million. The Obstetrics Division serves the region as demonstrated by over 12,000 clinic visits as well as approximately 2,000-plus hospital discharges per year. There were 1960 live births at Jacobi Medical Center during 2015 with 1373 of these births to Black and Hispanic women.

Obstetrical care is provided by 22 licensed midwives at Jacobi Medical Center as well as by over 40 obstetricians. There are adequate numbers of bilingual licensed midwives to work with Co-Investigator [name], CNM, RN to provide group prenatal care. There is an excellent working relationship between obstetrical and pediatric care providers and both obstetrical and pediatric care providers are interested and supportive of this study.

Jacobi Medical Center offers a number of other resources to its obstetrical patients receiving care in the Women's Health Practice. There are two Women's Health Patient Educators, who provide a weekly class series, with a new curriculum each month covering topics like childbirth education, infant safety and postpartum care. Women are encouraged to attend all of them starting in the 7th month of pregnancy. The Midwifery staff offer monthly Childbirth Education classes. There are two full-time IBCLC-certified Lactation Consultants available to patients in both the group and individual setting to assist with the initiation and continuation of breastfeeding. Jacobi has a specialized Adolescent Obstetric Practice to meet the needs of young mothers-to-be and Family Planning Services. Pregnant women and new mothers, who meet income eligibility criteria, are assessed by a healthcare professional for WIC eligibility which would provide them access to nutrition advice, breastfeeding support, nutritious food, and other services.

The Research Center of the NBHN is located at Jacobi Medical Center and has demonstrated its proficiency in sound, meticulous, efficient and ethical clinical investigation. Presently running more than 40 protocols funded by the National Institutes of Health, numerous private foundations, and many industry and trade organizations, including the largest Pediatric HIV clinical trial group in the country, the Center meets its mission of finding new and better ways to help patients through world-class clinical research and will provide support for this current application. The Center is presently conducting investigations by more than 30 researchers representing every clinical specialty area offered by the NBHN Network. It employs two full time regulatory affairs managers who maintain strict adherence to the most stringent submission requirements and deadlines, and twelve full-time Research Coordinators. A unique arrangement with two approved Investigational Review Boards facilitates the review and approval process. A research coordinator with experience in obstetrical research and the ability to speak Spanish will be hired to participate in data collection.

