### **Analysis plan.**

**Data management:** Survey data will be obtained using paper and pencil surveys and at each site all surveys will be scanned using Remark software to ensure accuracy and avoid the necessity of double data entry. Fitbit data will be uploaded using Bluetooth technology at each data point (with T0 baseline data being collected between screening and the first group prenatal care session) and entered into an Excel database. Data from the 24 hour diet recalls will be manually entered at each site into Food Processor and then exported into an Excel file for data analyses. At each visit, weights will be recorded. Obstetrical chart data will be extracted at each site. [name] will merge the Ohio and New York data files, perform data cleaning, construct analytic variables, assess psychometrics and conduct both interim and final analyses.

**Data Analysis:** Preliminary analyses: Statistical analyses of these data must not only demonstrate the efficacy

07/30/2021

of the COPE-P intervention, but also map the trajectories of group differences over time, and identify subgroup differences. Analysis will begin with characterization of the sample with descriptive statistics that identify differences between the COPE-P and PregnancyPlus groups 1) evident at baseline, despite randomization and 2) between groups due to differential attrition. Data will be screened for normality, outliers, and homogeneity. Appropriate nonparametric analyses will be considered in situations of irresolvable heterogeneity. We will evaluate the psychometric qualities (reliability, convergent and discriminant validity) of the scales, employing both exploratory factor analyses and SEM measurement models. Descriptive statistics will be used to summarize the sample characteristics and distribution of each variable. Missing Data. All data analyses will be completed as intention to treat analyses (i.e., individuals analyzed by group according to original random assignment, without regard to adherence to the intervention). Missing data will be imputed, when appropriate, using multiple imputation in SAS v9.4 PROC MI.

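### At the stated 30% attrition, the Jacobi ceiling of 236 women yields about 165 completers, 17 short of the 182 required

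*Combined protocol and SAP*

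**What the plan says.** The Overview of the design states the Jacobi aim as to "achieve our target of 182 Black or Hispanic women who complete the study". The same sentence continues: "accounting for a 30% attrition rate, we will enroll up to 236 women who screen in at Jacobi Medical Center". On the supply of women it says: "We will consent and screen up to 700 women, knowing that approximately half will screen out".

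The Sampling paragraph confirms that 182 counts women who finish, not women enrolled: "A completed sample size of 182 Black and Hispanic women from JMC in the Bronx". It adds the second site: "182 Black and Hispanic women from OSU Total Health and Wellness clinics will be required to meet the determined sample size of 364 total". The power claim follows directly: "This will have greater than 80% power to detect small to moderate effects".

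The Analysis plan specifies intention to treat and says: "Missing data will be imputed, when appropriate, using multiple imputation in SAS v9.4 PROC MI". No section gives another attrition rate or a higher enrolment figure for Jacobi, and none gives an enrolment figure for the second site.

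**The concern.** An attrition rate is the share of enrolled women who are lost, so the enrolment target is the completer target divided by one minus that rate. The stated 236 is too small for that. It is close to what results from adding 30% to the completer target, a common slip that always gives too small a number.

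The 182 at Jacobi is half of the sample that the plan calls required, and the power statement is attached to that sample. Because 236 is an upper limit, 165 is the best expected result at the plan's own attrition rate; enrolling fewer women widens the gap. A trial that meets its recruitment ceiling and sees exactly the dropout it planned for would still be expected to miss its completer target.

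**Working it through.** **Inputs**

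- Completer target at Jacobi: 182 (Overview of the design; Sampling)
- Attrition: 30% (Overview of the design)
- Enrolment ceiling at Jacobi: 236 (Overview of the design)
- Completers over both sites: 364 (Sampling)
- Screening: up to 700, about half screening out (Overview of the design)

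**Reproducing the plan's figure.** The protocol shows no formula. Adding 30% to the target gives 182 × 1.30 = 236.6, which matches 236 when rounded down. That origin is an inference.

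**Check of the sentence**

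- Expected completers: 236 × (1 − 0.30) = 165.2
- Shortfall: 182 − 165.2 = 16.8, or 16.8 / 182 = 9.2% of the Jacobi target and 16.8 / 364 = 4.6% of the two-site total
- Enrolment needed: 182 / (1 − 0.30) = 260, which is 24 above the ceiling
- Attrition at which 236 just suffices: 1 − 182 / 236 = 22.9%

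**Chance of reaching 182 anyway.** Assume women drop out independently of each other. The binomial probability of 182 or more completers from 236 is then 0.9% at 30% attrition and about 25% at 25% attrition.

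**Illustration of the effect on power.** This is not the plan's model. It assumes a two-sided 5% test comparing two equal arms at individual level, no clustering, and no information from dropouts. Take an effect with exactly 80% power at 364 completers and scale the noncentrality, 1.960 + 0.842 = 2.802, by √(n / 364):

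| Case | Completers | Power | Power needed at 364 to keep 80% |
|---|---|---|---|
| Only Jacobi short | 165.2 + 182 = 347.2 | 78.1% | 81.8% |
| Both sites equally short (assumption) | 2 × 165.2 = 330.4 | 76.1% | 83.7% |

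**Room for 260.** Half of 700 is about 350 women screening in, which covers 260 if the 700 applies to Jacobi alone. That reading is inferred: 350 could not supply two sites at 236 each (472). If all 30 groups are at Jacobi (assumption), mean group size would rise from 236 / 30 = 7.9 to 260 / 30 = 8.7. The protocol sets a minimum of six women per group and no maximum.

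**The case against.** The strongest reply concedes the arithmetic and disputes its consequence. The Sampling paragraph counts four data collection points per woman, and the Analysis plan describes multiple imputation and random-effects models, so a woman who leaves early still contributes. The illustration above starts at exactly 80%, which guarantees a fall below it.

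A repeated-measures check shows how little may be lost. Assume an effect of 0.25 SD (one reading of the unclear effect size under Sampling), equal correlation of 0.3 to 0.7 between visits, no clustering, and a baseline-adjusted mean of three follow-ups. Power is then about 95–99% at 364 completers, 94–99% at 347 and 93–98% at 330. With a single baseline-adjusted follow-up and correlations of 0.3, 0.5 and 0.7, it is about 71%, 79% and 92% at 364, and 69%, 77% and 90% at 347. In none of these scenarios does the shortfall move power across 80%.

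It can also be said that the 30% was meant as a loose over-enrolment allowance, which would cover a true loss of 22.9%.

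The point about power stands: the loss is probably modest, and the unstated model inputs matter more than 17 women. The reading as an allowance does not stand, because the text calls the figure an attrition rate. Nor do imputation and mixed models reconcile the numbers: the plan defines its requirement as completers, and 165 is not 182.

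**Conclusion.** The concern holds. The sentence is wrong as written: its three figures are mutually inconsistent, and at the stated attrition rate Jacobi is expected to finish about 17 women short (9% of its target, 4.6% of the two-site total). This needs no assumption beyond the ordinary meaning of an attrition rate. The target remains reachable if attrition turns out to be 22.9% or less.

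The probabilities of reaching 182 rest on independent dropout. The power figures rest on the simplified models described and, for 330 completers, on an assumed equal shortfall at the second site. Loss of the claimed 80% power is not shown. The finding applies to Jacobi only.

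**What to change.** Restate the figures so that they agree, in one of these ways:

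1. Keep 236 and 182, state that this requires attrition of at most 22.9%, and justify that rate from data rather than deriving it from the ceiling.
2. Keep 236 and 30%, state about 165 expected completers at Jacobi, and recompute the power under Sampling from the resulting total, using the plan's own model.
3. Keep 182 and 30%, and raise the ceiling to 260.

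The first costs a wording change and a justification. The second costs one power calculation, but the Sampling paragraph gives no standard deviation, correlation or intracluster correlation, so the team must supply and report these. The third adds 24 women at Jacobi, which the screening figures appear able to supply.

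It would also help to state the second site's enrolment figure and attrition rate, and to run the same check there before restating the total of 364.

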### Procedure.

After meeting inclusion criteria for the study, she will be given screening tools (General Anxiety Scale – GAD-7, Perceived Stress Scale – PSS, and the Edinburgh Postnatal Depression Scale – EPDS) to determine study participation.

If a potential participant scores:

- Greater than or equal to 10 on the General Anxiety Disorder 7-item scale (GAD-7)
- Or greater than or equal to 20 on the Perceived Stress Scale (PSS)
- Or a cut-off score of 10 on the Edinburgh Postnatal Depression Scale (EPDS)

They will be eligible to participate in the study. For the GAD-7 a score of  $\geq$  to 10 indicates moderate anxiety and maximizes sensitivity and specificity, for the PSS, a score of 20 or greater is the high-stress cut-off and a cut-off score of 10 on the EPDS is suggested to indicate moderate depressive symptoms in pregnant women.

If a **participant does not screen** into the study, she will be thanked for her time and interest and paid \$10.00 for her participation in the screening process.

07/30/2021

If a **participant does screen into the study**, she will provide further baseline data at this point which includes: demographic and personal information, weight from clinic scale, a 24 hour diet recall, the Healthy Lifestyle Beliefs Scale and the Healthy Lifestyle Behaviors Scale.

A participant will then be assigned to the next available group based on fetal gestational age (groups having been scheduled and previously randomized as intervention or control as described above). Participants will then be given an appointment for their first group prenatal care session and a Fitbit Flex 2, with instructions on how to immediately begin using the Fitbit (to provide baseline data that will be uploaded at the first group session) and a Fitbit number (for confidentiality) so that they can compare with other pregnant women. All participants will receive \$30.00 for at the baseline visit, **T0**.

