
Should any of the outcomes need to be dichotomized (i.e., present vs. absent), we will fit a multi-level random effects logistic regression models with time-varying covariates. The basic model, to which we will add our controls and predictors, can be written: where  $i$  indexes participants,  $t$  indexes time, COPE-P is an indicator of the intervention group, COPE-P x Time is the intervention by time interaction,  $X_k$  is a set of time-varying covariates measured for each participant  $i$  at time  $t$  and  $u_i$  is participant-specific error term. The interaction term COPE-P x Time is the test of the effectiveness of the COPE-P program. If successful, the regression coefficient will be negative, indicating that the modeled probability of psychological symptoms declined more

07/30/2021

rapidly with time in the COPE-P group than they did in the PregnancyPlus group. We will fit these models using SAS 9.4 (Proc NLMIXED).

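### Whole prenatal-care groups are randomised, but no described analysis accounts for the group and the power statement shows no allowance for it

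*Combined protocol and SAP*

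**What the plan says.** The Overview of the design in the combined protocol and SAP makes the prenatal-care group the unit of randomisation: "Each group within the 18-week time segment will be randomly assigned (using a sealed envelope technique) as either a COPE-P or PregnancyPlus group". At Jacobi, "for each 18-week time segment, there will be two control groups and two intervention groups". It plans 30 groups of at least six women, split by language: "There will be 22 English speaking groups and 8 Spanish-speaking groups".

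Women are not randomised individually. Under Procedure, "A participant will then be assigned to the next available group based on fetal gestational age", and the Overview adds "groups having been scheduled and previously randomized as intervention or control as described above".

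The Analysis plan never returns to that unit:

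- Hypothesis-driven analyses gives independent and paired t-tests, ANCOVA and repeated-measures ANCOVA as examples for the primary outcomes (healthy lifestyle behaviours, anxiety, stress, depressive symptoms).
- The growth model for continuous outcomes has two levels, visits within participants, with random subject intercepts and time trends. Its intervention-group predictor is the arm.
- The logistic model, used if an outcome is dichotomised, is indexed by participant and time, and its random term "is participant-specific error term". There, "The interaction term COPE-P x Time is the test of the effectiveness of the COPE-P program".

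The power statement under Sampling counts 364 completers and about 1,450 observations. It gives no ICC, design effect or number of groups.

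**The concern.** When intact groups are randomised, women in one group share an arm and may also share influences on outcome. An analysis that treats them as independent credits the arm comparison with more information than it has. Standard errors are too small, intervals too narrow, and the nominal 5% error rate is exceeded.

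Within-group correlation is plausible here at two points in time. Groups are formed by language, which could make women alike from baseline. They then share six sessions and the midwives who lead them. In COPE-P Session 3, "the group problem solves positive strategies to deal with depression, anxiety, and stress", and those symptoms are primary outcomes. Timing matters because a constant group effect cancels from a change over time, and one that arises after T0 does not.

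At stake are the between-arm conclusions on four primary outcomes, which Hypothesis 1a claims at three follow-up times.

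**Working it through.** **The plan's own figure.** The claim of more than 80% power comes without test, sidedness or within-person correlation. Assume that the stated effect of 25 means 0.25 SD, with 182 women per arm and a two-sided 5% test.

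- Single visit: 0.25/√(2/182) = 2.385, so power = Φ(2.385 − 1.96) = 66.5%.
- Baseline-adjusted mean of three follow-up visits, within-person correlation r = .5: variance v = (1 + 2r)/3 − r² = .4167. Then 0.25/√(2 × .4167/182) = 3.69, and power is 95.9%.

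The claim can thus be met or missed depending on inputs that the documents omit. Neither calculation contains a clustering term.

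**Inputs for the check.** Completers per group: m = 182/30 = 6.07, taking the 30 groups as Jacobi's and the second site as similar (its randomisation is not described). ICC .01/.02/.05/.10 is assumed. The outcome is continuous and there is no segment effect unless stated. With DE the design effect, the true error of a test that ignores groups is 2[1 − Φ(1.96/√DE)].

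**Single visit.** DE = 1 + (m − 1) × ICC.

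| ICC | DE | True type I error | Effective N = 364/DE |
|---|---|---|---|
| .01 | 1.051 | .056 | 346 |
| .02 | 1.101 | .062 | 331 |
| .05 | 1.253 | .080 | 290 |
| .10 | 1.507 | .110 | 242 |

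Simulation (60 groups of 6, 20,000 runs per cell, constant group effect) gave .077/.106 at ICC .05/.10.

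**Three-visit mean adjusted for baseline, r = .5, ICC .05/.10.**

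- Group effect constant from baseline: adjustment leaves a fraction (1 − r) of it. DE = 1 + (m − 1) × ICC × (1 − r)²/v = 1.152/1.304, so error is .068/.086 (simulated .066/.086).
- Group effect arising after T0 and persisting: DE = 1 + (m − 1) × ICC/v = 1.608/2.216 gives .122/.188. This leaves the added group variance out of the denominator. With v + ICC there, DE = 1.543/1.981 and error is .115/.164. Simulation gave .119/.170. About .12/.17 is the fair figure.

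**COPE-P x Time, treated as a linear slope over four visits.** The weights are −.3, −.1, .1, .3, with squares summing to .2, so a woman's slope variance is .2 × (1 − r) = .10 at r = .5.

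- Constant group effect: the weights sum to zero, the effect cancels, and error stays at 5% (simulated .051/.050).
- After T0: the last three weights sum to .3, so the group's slope variance is .09 × ICC. DE = 1 + (m − 1) × .09 × ICC/.10 = 1.228/1.456, and error is .077/.104.
- The planned continuous model also lets women's own slopes vary. If that adds .05 or .10 (assumed) to the .10, error falls to .068/.086 or .063/.077.

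**Segment effects.** The 2-versus-2 allocation cancels a segment effect from the arm difference, while an unstratified test still counts it as noise. With group variance g and segment variance s, single-visit DE = 1 + (m − 1)g − s. Error therefore exceeds 5% only if (m − 1)g > s. At m = 6 and g = .01, s = .06 gives DE = .99 and error .049; s = .10 gives DE = .95 and error .044. With g = s = .05, simulated error was still .076.

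**The case against.** The strongest reply is that the inflation may be negligible. No ICC is available, groups are small, sessions may be moved to virtual or 1:1 delivery, and segment effects can offset a weak group effect. All of that stands: at ICC .01 to .02 a single-visit test runs at about .056 to .062. But without a stated ICC the sponsor cannot show that the effect is small, and changing the delivery mode does not change what was randomised.

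Second, the model equations cannot be read in the text reviewed, so a group term might sit there. The sponsor should confirm. The surrounding prose defines only participant-level random effects. The covariance-structure selection concerns a woman's own responses over time. The mention of levels of analysis concerns mediation, in a model with only the visit and participant levels.

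A reader might infer more than the documents support:

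- **That power is below 80%.** Not shown. Under the three-visit adjusted analysis above, the simple design effects at ICC .05 leave about 93% (constant effect) or 83% (after T0). It falls to about 70% only in the after-T0 case at ICC .10.
- **That every test is inflated.** COPE-P x Time is unaffected by a constant group effect, and correlation due only to a shared segment causes no inflation. COPE-P x Time is named as the test of effectiveness only for the logistic model, whereas the slope figures here are for a continuous outcome.
- **That there are about 12 women per group.** If the 30 groups served both sites, m = 364/30 = 12.1 and single-visit error would be .063/.076/.116/.178. But the 30 groups are given beside Jacobi's own targets, and 182/30 fits the minimum of six better.

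**Conclusion.** The point holds and should be fixed before analysis. Confidence is high that the described analyses omit the randomised unit and that the power statement shows no allowance for it. The size of the effect is uncertain and rests on assumed ICCs, about 6 completers per group, r = .5 and no segment effect.

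Under those assumptions, at ICC .05/.10, the nominal 5% becomes about .08/.11 for a single visit. For a baseline-adjusted three-visit mean it is about .07/.09 if the group effect is constant and .12/.17 if it arises after T0. For COPE-P x Time it is 5% if constant, and at most about .077/.104 if after T0. The stated power is unsupported as regards grouping; it is not shown to be wrong.

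**What to change.** In every between-arm comparison (single-visit, averaged, arm-by-time, logistic), account for the prenatal-care group as originally assigned, including women moved to virtual or 1:1 delivery. Either of these will do, with between-group degrees of freedom:

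- a group random intercept plus a group-by-time random effect; or
- cluster-robust variance with a small-sample correction.

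The group-by-time term matters because the timing of the effect is unknown. With a group intercept alone and an after-T0 effect, simulated error for COPE-P x Time stayed at about .075/.095 at ICC .05/.10 (2,000 runs each). With a group variance fitted to each tested quantity and 58 degrees of freedom (60 groups less 2), simulated error was .041 to .050. The joint, robust and logistic versions were not simulated.

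Also:

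- Do not base between-arm inference on t-tests or ANCOVA that ignore the group. Paired within-arm tests are not the issue.
- Enter the 18-week segment as a stratum if segment differences are expected.
- Include the group in the PROC MI imputation model.
- Restate the power under Sampling with an ICC range, the number and size of groups across both sites, the test and the within-person correlation.

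**Cost.** SAP wording, changed model specifications and extra imputation work. Single-visit intervals widen by √DE − 1, about 2/5/12/23% at ICC .01/.02/.05/.10. At ICC .05/.10, three-visit adjusted intervals widen by about 7/14% if the effect is constant, or 24–27%/41–49% if it arises after T0 (square roots of the two pairs of design effects above).

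If the true ICC is zero, the tests are slightly conservative (simulated .042 for a single visit and .037 for COPE-P x Time, 60 groups of 6). If correlation is only at segment level, a group term without the stratum is more so: .024/.013 for a single visit at segment correlation .05/.10, against .037/.037 with the stratum. In a 15-segment layout the stratum uses 14 of the 58 degrees of freedom. The stated power will look less favourable; no extra enrolment is proposed.
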